#### Secondary Goals:

1. Assess the proportion of mechanically ventilated, critically ill patients, with or without primary neurological injury, who could benefit and operate an eye-movement-tracking device as a means of communication.
2. Assess the type and length of the use done by the patient. For example, we will monitor how long a patient wears the device, uses it, and for what purpose (communication, call for help or entertainment).
3. Assess the EyeControl device as a diagnostic/monitoring tool for delirium in comparison to the bedside nurse assessment. Specifically, the device will record times of wakefulness for each 24h period of time, and will test for delirium using CAM-ICU. The later will be correlated with a live, verbal assessment done by a study team member.
4. Assess patient proficiency in device operation through daily orientation questionnaire.
5. Assess the change in level of frustration and discomfort patients and families feel in relation to communication with and without the device. These will be assessed by a questionnaire given to patients and families near their discharge.
6. Explore possible correlation between eye movements and clinical events by evaluating photographs of the eyes at the times of these events.

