#### Secondary goals:

1. Assess the safety, tolerability, and ease of use of the EyeControl device; Specifically, we will assess on a daily basis for any adverse events related to the device. We will also document need for re-training on the device as a marker for ease of use.
2. Measure the length and intensity of use for communication and call for help; Intensity will be measured by the number of times the device is used and for which purpose as a categorical measure (eg, call for help, talk using predefined sentences, communicate using letter by letter dictation etc).
3. Correlate between the monitoring data and clinical data: the device will assess CAM-ICU independently, and a study team member will repeat this analysis and the documented results will be documented. We will also track any clinical decision making based on wakefulness time information (for example a decision to add melatonin agonist to promote sleep) ;
4. Measure the cognitive and functional long-term outcomes, by phone questioners, to be done in a blinded fashion at 6 months from ICU discharge.

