- b. Wakefulness monitoring—the device will record the times in which the patient is awake by monitoring when the patient's eyes are open. This data will later be correlated with outcome measures such as delirium, LOS, and functional outcome. Changes in wakefulness time will also be correlated with ICU interventions such as adding a melatonin-agonist to promote sleep.
- c. CAM-ICU validation—every shift, after the nurse and/or study team member assesses CAM-ICU, the device will repeat the test by using multiple-choice questions and ask the patient to choose the correct answers by blinking. We will later correlate the device's results with the nursing/study team ones.
- d. Reorientation – at a defined time interval, if the patient's eyes will be open, the device will read the patient the current date/time/location.
- e. Entertainment – patients will have the option to listen to music.
- f. Family communication – Families will be supplied with a patient-unique link to record audio messages which the patient will be able to listen to through the device.

To address the secondary goal of proficiency with device operation, we will administer a daily orientation questionnaire via the device. If a patient fails this proficiency check, study staff will perform a device re-training module. The frequency and amount of necessary re-training will be captured as another data parameter.

During the study, we will collect clinical information from the patient's chart including: demographics, diagnoses, use of sedatives or medications that could change cognitive function, nursing charting (including neurological assessment), laboratory results, days on the ventilator, procedures, discharge destination, mortality, and functional outcome. All of these will be taken into account for the final analysis of the study. For example, this data could help us better identify which patients used the device more than others and which could benefit from its monitoring properties apart from its communication function.

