1. Assess the safety, tolerability, and ease of use of the EyeControl device. This will be achieved by daily review of advance events, and ask patients, families and clinical team regarding challenges of use.
2. Measure the length and intensity of use; We will measure time to first activation, as detailed under the primary goal of the first step, and on a daily basis we will collect data from the device including the number of hours a day the device was worn, how many times it was used for communication, and the type of communication (eg use of predefined sentences, call for help, using new sentences by dictation, entertainment listening etc).
3. Correlate between the monitoring data and clinical data, specifically validate CAM-ICU with nursing and/or study team independent assessment; and correlating wakefulness time with ICU interventions; We will collect from the device on a daily basis the times when the patient has his or hers eyes open, as a marker of wakefulness. We will also record interventions related to sleep and wake cycles, such as administration of

Melatonin or Melatonin agonists, night time antipsychotics, benzodiazepines etc. We will also perform a correlation between the device independent assessment of CAM-ICU, and the clinical team assessment.

- Measure the cognitive and functional long-term outcomes, by phone questioners, to be done in a blinded fashion at 6 months from ICU discharge. This will include a pre-defined battery of tests, as detailed under the Long-Term Outcomes (LTO) Battery section below.

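### The device's CAM-ICU is to be validated by correlation alone, which does not show whether it misses or over-calls delirium, and dependence between repeated pairs from one patient is not addressed

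*Combined protocol and SAP*

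**What the plan says.** The aim is diagnostic in both steps.

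- **Step 1, secondary goal 3:** "Assess the EyeControl device as a diagnostic/monitoring tool for delirium in comparison to the bedside nurse assessment". The analysis follows in the same item: "The later will be correlated with a live, verbal assessment done by a study team member".
- **Step 1 procedures, item c (headed as CAM-ICU validation):** "every shift, after the nurse and/or study team member assesses CAM-ICU, the device will repeat the test by using multiple-choice questions", and then "We will later correlate the device's results with the nursing/study team ones".
- **Step 2, secondary goal 3:** also framed as a correlation, with the procedure "the device will assess CAM-ICU independently, and a study team member will repeat this analysis".
- **Step 2, secondary outcome 3:** "specifically validate CAM-ICU with nursing and/or study team independent assessment", and then "We will also perform a correlation between the device independent assessment of CAM-ICU, and the clinical team assessment".

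No coefficient is named. Sensitivity, specificity, predictive values, kappa, percent agreement and an acceptance threshold appear nowhere.

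The Statistical Analysis Plan section does not fill the gap. Step 1 is descriptive. Step 2 gives generic rules by type of variable, and the only clustering it handles is by ICU.

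The human comparator also varies: bedside nurse and study team member within one Step 1 goal, nurse and/or study team elsewhere, and the clinical team in the Step 2 outcome. In Step 2, CAM-ICU is charted as undetermined when RASS is below -1. The plan does not say how such results enter the paired comparison.

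**The concern.** The question is whether a yes/no result from the device can stand in for a yes/no result from a trained assessor. A user needs to know how much delirium the device misses and how often it raises a false alarm. A correlation combines the two into one number that is symmetric in the direction of error, so a result obtained exactly as planned could not separate an insensitive device from an over-calling one.

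Repeated testing adds a second gap. Pairs from one patient are likely to be alike, because the same person handles the device well or badly each time. If an analyst took every pair as independent, the interval would be too narrow, and nothing in the plan guards against that.

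Third, the wording suggests human first in Step 1 and device first in Step 2. The second test is open to practice effects and to fluctuation of delirium. If a human goes second, it is also open to knowledge of the device result. Without a stated order and concealment, it is unclear which test carries these effects.

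**Working it through.** The plan states no sample size, precision target or threshold for this validation, so there is no figure to reproduce. The two calculations below are illustrations.

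**1. What a correlation between two binary results can hide**

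Inputs: delirium prevalence p, sensitivity Se, specificity Sp. The Sample Size section cites a delirium rate of about 50% from an earlier cohort. Using 50% as the share of assessments that are positive is an assumption; 30% is shown as an alternative.

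Cells: a = p·Se, b = (1−p)(1−Sp), c = p(1−Se), d = (1−p)Sp. The share the device calls positive is r = a + b.

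phi = (ad − bc) / √[r(1−r)p(1−p)]

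kappa = (po − pe)/(1 − pe), with po = a + d and pe = rp + (1−r)(1−p)

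For Se = 0.53, Sp = 1.00 and p = 0.5: a = 0.265, b = 0, c = 0.235, d = 0.5, r = 0.265. So phi = 0.1325/√(0.265 × 0.735 × 0.25) = 0.60 and kappa = (0.765 − 0.5)/0.5 = 0.53.

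| Prevalence | Se | Sp | Device positive | phi | kappa |
|---|---|---|---|---|---|
| 50% | 0.53 | 1.00 | 26.5% | 0.60 | 0.53 |
| 50% | 0.80 | 0.80 | 50.0% | 0.60 | 0.60 |
| 50% | 1.00 | 0.53 | 73.5% | 0.60 | 0.53 |
| 30% | 0.50 | 0.98 | 16.2% | 0.60 | 0.56 |
| 30% | 1.00 | 0.65 | 54.3% | 0.60 | 0.53 |

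At 50% prevalence, one value of phi covers a device that misses 47% of delirium and one that wrongly flags 47% of non-delirious assessments. Kappa is 0.53 in both of those cases, so kappa alone does not give the direction either. Sensitivity and specificity do.

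**2. Repeated pairs**

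Inputs: m pairs per patient and a within-patient correlation ICC. Both are assumptions: m = 6 to 16, ICC = 0.3 to 0.7. As a rough upper guide to m, the background section gives a mean of 8.6 ventilator days. Two tests a day (the Schedule of Events has CAM-ICU every 12 hours) would give 8.6 × 2 = 17.2.

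Design effect = 1 + (m − 1)·ICC. An interval that ignores clustering is too narrow by the square root of this.

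- m = 6, ICC = 0.3: 1 + 5 × 0.3 = 2.5; √2.5 = 1.6
- m = 16, ICC = 0.7: 1 + 15 × 0.7 = 11.5; √11.5 = 3.4

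Sensitivity uses only reference-positive pairs and specificity only reference-negative pairs. Halving m to 3 to 8:

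- m = 3, ICC = 0.3: 1 + 2 × 0.3 = 1.6; √1.6 = 1.3
- m = 8, ICC = 0.7: 1 + 7 × 0.7 = 5.9; √5.9 = 2.4

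**3. Test order**

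Step 1, item c, has the device repeating after the nurse or study team. Step 2, secondary goal 3, has a study team member repeating what the device did. Step 2, secondary outcome 3, gives no order. Step 2 is described as resembling Step 1 in screening and enrolment, which leaves open whether the CAM-ICU procedure carries over.

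**The case against.** **Correlation may be loose wording.** No coefficient is named, the text also speaks of validation and comparison, and the same verb covers wakefulness against ICU interventions. The synopsis treats the burn-in work on this feature as proof of concept. This is fair, and it is why the point is minor. But correlation is the only analysis named in any of the four places, and the SAP offers nothing else.

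**Correlation is not unrelated to agreement.** A reader might infer that it says nothing about agreement. That is too strong. When both raters call the same share positive, phi equals kappa, as in the 0.80/0.80 row. A high phi also limits how bad the device can be: at 50% prevalence, phi of 0.80 needs sensitivity of at least about 0.78. What stands is narrower: unequal positive rates are what a validation must detect, and phi does not show which way they differ.

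**Independence of pairs is not stated.** A reader might infer that the plan will treat pairs as independent and so overstate precision. The documents do not say so and promise no interval for this correlation. They are silent. The number of pairs is also uncertain: pairs arise only while the patient wears the device and can be tested, and the frequency of the device's test in Step 2 is not given.

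**The orders may be intended.** A reader might infer a contradiction between the two procedures. They belong to different steps, and repeating an analysis in the Step 2 goal could mean a duplicate assessment with no sequence implied. What stands is that the passages read differently, no reason is given, and concealment of the first result is not stated beyond the word independent.

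**Conclusion.** The point holds as a minor one. The plan's only named analysis for a diagnostic aim does not show the direction of error: at 50% prevalence, phi of 0.60 fits anything from sensitivity/specificity of 0.53/1.00 to 1.00/0.53. That result follows from the algebra; only the prevalence and the chosen phi are illustrative, and 30% prevalence gives a similar spread.

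Within-patient dependence is not addressed. The factor of 1.6 to 3.4, or 1.3 to 2.4 with half the pairs, rests wholly on assumed pairs per patient and ICC. It shows why the matter needs a rule and is not an estimate for this trial.

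A reader might also infer that the primary endpoint is compromised, because CAM-ICU positivity defines delirium there. The documents do not show that device results feed that endpoint, so the primary comparison is not shown to be affected.

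**What to change.** For the CAM-ICU comparison only, replace correlation in Step 1 secondary goal 3, Step 1 item c, Step 2 secondary goal 3 and Step 2 secondary outcome 3. Leave the wakefulness correlations as they are. The SAP section should carry the same text, for example:

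> The device CAM-ICU will be compared with the CAM-ICU by [one named human assessor] from the same shift, among pairs in which both results are determinate. Sensitivity, specificity and Cohen's kappa will be reported with 95% confidence intervals from a bootstrap that resamples patients (or from GEE clustered by patient). The number of pairs excluded as undetermined will be given.

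State the intended test order for each step, so that Step 1 item c and Step 2 secondary goal 3 can be read together, and keep the second assessor unaware of the first result.

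The cost is SAP and procedure wording, slightly more analysis, and wider intervals than a pair-level analysis would give. The paired results are already to be collected, and no extra patients are needed.

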## SUBJECT FLOW SCHEMA (STEP 2)

## STUDY POPULATION AND SUBJECT SELECTION

Potential study population includes any patients admitted to the ICU. At Emory University Hospital, there are 121 active ICU beds as described in table 1.

Table 1: Intensive care units (ICUs) at Emory University Hospital

ICU	No. of Beds
Medical ICU (MICU, 5T-N)	17
Surgical ICU (SICU, 5T-S)	23
Neuroscience ICU (2D/2G)	40
Cardiothoracic surgery ICU (5E)	20
Cardiac ICU (CCU, 3G/4G)	14
Respiratory ICU (4A, 6A, 5G, 6G)	28
Total	142

## PARTICIPANT SELECTION AND SAMPLE SIZE

According to our retrospective analysis, we intend to screen all admissions to all the ICUs at EUH on a daily basis and identify patients who were ventilated for at least two days as the initial screening. For those who meet these criteria, a further investigation into the patients' chart will occur by the study team to identify the inclusion/exclusion criteria. We will obtain a de-identified list of screen failures and the reason for the failure.

### INCLUSION CRITERIA

- Intensive Care Unit (ICU) Admission
- Mechanically ventilated for at least 24 hours
- RASS between -1 to 1 at the time of screening (Note: minimal sedation is allowed including low-dose Fentanyl, Dexmedetomidine, Ketamine, Propofol, etc., as long as the RASS is in the predefined range).

### EXCLUSION CRITERIA

- < 18 years of age
- Not admitted to the ICU
- Inability to follow commands during screening (at a minimum: open and close eyes, move eyes to one side or the other).
- Known cerebral injury (acute or chronic) in the dominant hemisphere concerning for aphasia on clinical assessment
- Significant pre-existing neurologic (i.e., dementia and/or cognitive deficiencies), hearing loss (with inability to hear through a bone-conduction speaker), psychiatric, or baseline communication challenges that would confound outcomes assessments
- Inability to blink or move eyes for any reason
- Prisoner or incarceration
- Inability or unwillingness to provide informed consent
- Unwillingness to be contacted for follow-up

Patients who meet the inclusion and do not meet any exclusion criteria will be approached for consent, as will be described below.

## SAMPLE SIZE

From our retrospective analysis (described in the introduction), we expect about 130 patients per month for the initial screening (ventilated for at least two days). The same patient could be ineligible on a certain day, but become eligible later in the admission (e.g., due to the severity of the illness, the patient is deeply sedated for the first few days, and later sedation is weaned). This will allow us to recruit more patients, at different time points of their admission. Even with this in mind, it would be reasonable to assume that about half of these initially screened patients will not be eligible at any point of their admission due to any one of the exclusion criteria. Of those who will be eligible, we expect a high rate of consent, due to the low risk and the potential benefit of using the device while in the ICU. We therefore expect a rate of about 30 patients a month to be enrolled.

For the first step, we will plan to enroll up to 60 patients, and at least a third of the sample will be from the neuroscience ICU, and specifically patients with an acute brain injury

Given that there are no prior data, there is no clear criteria that would justify a specific number. We believe that having 40 to 60 patients work with this new device would be sufficient to draw initial conclusions about its use and specific indications according to the study aims as stated above.

For the second part of the trial, power calculations are based on previously published BRAIN-ICU trial. In that observational trial patients had  $6.8 \pm 5.2$  delirium/coma-free days within the first 14 days of admission, with an overall rate of about 50% rate of delirium. For the present trial, we considered a 2 day reduction in the time spent delirious as clinically significant. Given these parameters, the present trial will require 248 patients ( $N = 124$  per arm) to achieve sufficient power (80%,  $\alpha = .05$ ) to detect a 2 day difference. In general, a sample size of 248 will provide sufficient power to detect a standardized mean difference of 0.38 (assuming minimal asymptotic relative efficiency of Mann-Whitney U test), an odds ratio of 2.14 for binary variables (assuming maximal variance for a binomial distribution), and a Cohen's  $f$  of 0.18.

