### STEP 2:

**Primary goal:** Measure the time spent alive and non-delirious in the ICU up to 14 days from randomization with EyeControl-based communication compared with the standard of care, in a randomized-controlled fashion.

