As part of its operation, the device captures photographs and video of the patient's eyes (figure 3). In addressing the secondary goal of potential correlation between eye behavior and clinical events, we will explore this possibility by evaluating photographs of the eyes at the times of clinical events (i.e. hypoxia, new onset shock, or new onset sepsis). The device will activate the image data collection only after 50 consecutive frames of eye-in-the-image. This should be a safety index to verify that the device is only recording the eye. It will stop recording immediately when non-eye-in-the-image occurs. Data processing to decide if an eye is in the image is done locally on the device, so eventually only images of eyes should be collected. All external image data processing will be done following deidentification of the data, using the patient code only as an identifier.

Figure 3. Example photographs captured by the EyeControl device.

No randomization or blinding is planned for this step of the study, and no samples are planned to be collected.

---

**STEP 2: MEASURE REDUCTION IN DELIRIUM-FREE AND ALIVE DAYS IN THE ICU WITH EYECONTROL-BASED COMMUNICATION COMPARED WITH THE STANDARD OF CARE.**

The second step will be similar to the operation of the first one, in terms of patient screening and enrolling. The main difference will be the randomization process. Patients will be randomized to use EyeControl for as much as they wish, versus the standard of care. Randomization will be done centrally, and will be stratified to the specific unit, gender and age, race and ethnicity.

The primary goal of the second step will be to measure the time spent alive and non-delirious in the ICU with EyeControl-based communication compared with the standard of care. Delirium will be defined as CAM-ICU positive, starting at day 1 of use (following the day of training), up to 14 days from randomization or ICU discharge, the earliest. However, patients could require moderate to deep sedation following randomization, for example due to new or evolving medical complication. Whenever the RASS is below (-1), CAM-ICU will not be measured, and will be charted as undetermined. Therefore, only days in which the patient will be CAM-ICU positive, will be counted towards the primary outcome. CAM-ICU positive days prior to randomization will not be counted towards the primary outcome.

[figure not shown]
The secondary outcomes will include the following:

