### Step 2:

Primary Outcome: The time spent alive and non-delirious in the ICU

Covariates/Confounders: age, gender, race, baseline education level, unit to which the patient was admitted to, need for tracheostomy, severity of illness by SOFA or APACHE score on admission and randomization day, categorical reason for admission (e.g. sepsis, ARDS, elective surgery, stroke etc), diagnosis of delirium prior to randomization and the presence of an acute central neurological injury.

Unadjusted Analyses: The time spent alive and non-delirious in the ICU will be evaluated using the stratified variant of the Mann-Whitney U test. In this analysis, patients will be stratified by ICU setting. For other variables, the unadjusted comparison will depend on the type of variable. In general, continuous variables will be compared using a Mann-Whitney U test and categorical variables will be compared using the  $\chi^2$  test.

Adjusted Analyses: The time spent alive and non-delirious in the ICU will be evaluated using a multi-level/mixed-effects quantile regression (median/50th percentile) while controlling for the previously listed covariates. The multi-level/mixed-effects model will be used to account for clustering within ICU setting. In the event that the regression fails to estimate properly, the covariates will be used to generate propensity scores and patients will be stratified into  $\geq 5$  propensity score strata. The time spent alive and non-delirious in the ICU will then be analyzed using the stratified variant of the Mann-Whitney U test. Analyses of the secondary outcomes will depend on the type of variable. Continuous variables will be analyzed using multi-level/mixed-effects quantile regressions (median/50th percentile), binary variable will be analyzed using multi-level/mixed-effects binary logistic regressions, ordinal scales will be analyzed using multi-level/mixed-effects ordinal (cumulative logit) logistic regressions.

Missing Data: In the event of substantial missing data, data will be imputed using a multiple imputation procedure. The type of procedure (e.g. fully conditional specification, hot decks etc.) and the number of imputed data sets will be determined by the amount of missing data and the pattern of missingness.

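### The 80% power for a 2-day difference is not tied to one defined Step 2 primary variable, because the plan states that variable in opposite directions and borrows its SD from a different one

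*Combined protocol and SAP*

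**What the plan says.** All references are to the combined protocol and SAP.

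**Primary variable.**
- Study Purpose, Step 2 primary goal: "Measure the time spent alive and non-delirious in the ICU up to 14 days from randomization".
- Statistical Analysis Plan, Step 2: "The time spent alive and non-delirious in the ICU will be evaluated using the stratified variant of the Mann-Whitney U test".
- Study Design and Methods, Step 2: the goal sentence also uses alive and non-delirious time. The counting rule that follows says "only days in which the patient will be CAM-ICU positive, will be counted towards the primary outcome", and the heading of the same section announces a reduction in days free of delirium.
- Synopsis, Outcome Measures: as printed, a count of days alive and with delirium, in the ICU and on the ventilator, ending at 14 days, extubation or ICU discharge.

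**Window and undetermined days.** The Step 2 design section defines delirium as CAM-ICU positive, "starting at day 1 of use (following the day of training), up to 14 days from randomization or ICU discharge, the earliest". It adds: "Whenever the RASS is below (-1), CAM-ICU will not be measured, and will be charted as undetermined".

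**Power.** The Sample Size section takes 6.8 ± 5.2 from an earlier observational study, described as "delirium/coma-free days within the first 14 days of admission, with an overall rate of about 50% rate of delirium". It sets the target in these words: "For the present trial, we considered a 2 day reduction in the time spent delirious as clinically significant". It then asks for 248 patients (124 per arm) for 80% power at alpha 0.05, and says this detects a "standardized mean difference of 0.38 (assuming minimal asymptotic relative efficiency of Mann-Whitney U test"). The synopsis gives 244 patients for Step 2.

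**The concern.** The SD, the effect and the analysed endpoint are three different quantities. Free days and delirious days are not mirror images within 14 days, since coma and death also remove free days. No section gives an SD for any Step 2 version of the endpoint or argues that 5.2 carries over.

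The larger problem is the endpoint itself. A programmer following the Step 2 counting rule and one following the SAP would build different datasets with opposite directions of benefit. If the choice stays open until data are available, it could change the conclusion. A null result would also be set against a claim of 80% power for 2 days that has not been shown for whichever version was analysed.

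**Working it through.** **1. Reproduce the plan's figure.** Inputs from the Sample Size section: difference 2, SD 5.2, alpha 0.05, power 80%. Two-sided testing is assumed because sidedness is not stated; a one-sided calculation gives about 97 per arm and does not match. The minimal Mann-Whitney efficiency is named but not printed; its value is 0.864.
- d = 2/5.2 = 0.385.
- Two-sample t-test: 107.09 per arm.
- 107.09/0.864 = 123.94, so 124 per arm and 248 in total. This is an exact match.
- Detectable d at 124 per arm: 0.3845, in line with the printed 0.38.
- The synopsis figure of 244 (122 per arm) gives 79.4% against 80.0% on the same inputs, so that discrepancy is editorial.

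**2. Compare the SD's source with the trial's endpoint.**

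| Feature | Source of the 5.2 | SAP / Study Purpose | Step 2 counting rule | Synopsis |
|---|---|---|---|---|
| Quantity | days free of delirium and coma | time alive, non-delirious, in ICU | CAM-ICU positive days | days alive and with delirium, as printed |
| Better is | more | more | fewer | fewer, as printed |
| Start | admission | randomization (Study Purpose) | day 1 of device use | randomization |
| End | 14 days | 14 days (Study Purpose), in-ICU time only | 14 days from randomization or ICU discharge | also extubation |
| Days with RASS below -1 | coma days not free | not stated | undetermined, so not counted | not stated |

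A control patient has no day of device use, so the start in the counting rule is undefined in one arm. Entry also requires RASS -1 to 1 and following commands. The source variable is therefore at best a rough proxy for the non-delirious version, and it is no proxy for CAM-ICU positive days.

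**3. A consequence of the in-ICU, non-delirious version.** Take two hypothetical patients. One leaves the ICU on day 5 without ever being delirious and scores at most 5. The other stays 14 days, 4 of them delirious, and scores 14 - 4 = 10. The patient who left sooner has the worse score.

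**4. How far power can move at 124 per arm.** These are simulated, unstratified Mann-Whitney tests on delirious days, with 50% of controls ever delirious. The shapes are assumptions, since the documents give none.
- *Shortening only.* Durations in delirious controls are uniform on 5 to 14 days, each cut by 4 days on the device. Means are 0.5 × 9.5 = 4.75 and 0.5 × 5.5 = 2.75, a difference of 2. Power is about 64%.
- *Prevention only.* Durations are uniform on 4 to 12 days, with the delirium rate halved. Means are 0.5 × 8 = 4 and 0.25 × 8 = 2, a difference of 2. Power is about 97%.

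**5. What 2 days would require.** If the device shortens delirium but prevents none, a 2-day mean difference over all patients equals 2 divided by the proportion delirious. The Sample Size section gives about 50%, so 2/0.50 = 4.0 days per delirious patient. The background section on ICU delirium gives 48-83%, so 2/0.48 = 4.2 down to 2/0.83 = 2.4 days.

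**The case against.** Borrowing an SD from a related published outcome is ordinary planning, and days free of delirium and coma is a sensible relative of alive, non-delirious time. The Sample Size section also speaks of a 2-day difference, which has no direction, and the goal sentence in the Step 2 design section agrees with the SAP. All of this stands. It means the SAP version is the most likely intention and that 5.2 is a usable rough guide to it. It does not remove the CAM-ICU positive counting rule, the arm-specific start, the synopsis version or the differing stopping points.

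A reader might go further in three ways that the documents do not support.
- *The trial is underpowered.* With no SD or distribution for the endpoint, this cannot be shown. A truncated count could have a smaller SD than 5.2, and the achievable difference could be smaller too.
- *Power can be read from the SD alone, with a worst case of 55% at the 14-day ceiling SD of 7.0.* An SD of 7.0 on 0-14 days needs half the values at 0 and half at 14; simulated power for that two-point variable is about 61%. The 0.864 floor applies to a pure shift of a continuous variable, not to a capped count with many zeros. In the shortening example the arm variances are 26.7 and 11.7, so the pooled SD is √19.2 = 4.4. The formula then gives above 90%, against about 64% simulated.
- *The extubation stop leaves a window of 8.6 - 2 = 6.6 days.* The mean of 8.6 ventilator days is uncapped and covers everyone ventilated for at least two days, a broader group than those eligible.

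**Conclusion.** The point holds as a failure to define the endpoint and link the power statement to it. The Step 2 primary variable is contradictory in direction, start and end, and the 80% for 2 days has not been established for any version of it. The 248 and the 0.38 are correct as a calculation for a shift alternative.

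The possible error is material in either direction: the same 2-day mean difference gave about 64% or about 97% power depending only on the assumed shapes and on whether delirium is shortened or prevented. Those two figures rest on the assumed shapes, 50% ever delirious and no stratification. They show sensitivity and do not estimate this trial's power. The finding that the sections conflict rests on the text alone. This should be settled before Step 2 opens.

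**What to change.** 1. **Choose one primary variable** and bring the synopsis, Study Purpose, Step 2 design section (including its heading), Sample Size and SAP into line with it. State one direction, a start that exists in both arms (for example randomization) and one end. Give rules for undetermined days, death and days after ICU discharge. If non-delirious time is kept, the count should not stop at ICU discharge or extubation in a way that gives a patient who leaves sooner a worse score.
2. **Restate the power.** Express the 2 days in that variable and direction. Keep 0.38 as the standardized figure for a shift alternative. Report power at 248 by simulating the stratified Mann-Whitney test on plausible distributions with zeros, ties and the 14-day cap. Cover prevention and shortening, and delirium rates over 48-83% including the 50% used for planning. Do not rely on a table by SD alone.
3. **Replace 244 with 248** in the synopsis.

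The cost is redrafting and a short simulation. The stated power may become less favourable. Restating it does not itself call for more patients; whether 248 is adequate can be judged only once the variable is fixed.
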